**STUDY SUMMARY/SYNOPSIS**

TITLE	A randomised controlled trial to evaluate the impact of thoracic PRehabilitation with Inspiratory Muscle tRaining cOmpared to Standard prEhabilitation in surgical lung cancer patients.
SHORT TITLE	PRIMROSE Trial
Protocol Version Number and Date	Standard Protocol Version Number 3.5 and date 03/02/25
Methodology	Type of study: randomised control trial
Study Duration	Two years
Study Centre	Cardiothoracic centre, Morriston Hospital
Objectives	To compare inspiratory muscle training (IMT) with standard Prehabilitation (Prehab) to Prehab alone, in lung cancer patients for surgery.
Number of Subjects/Patients	One hundred and thirty-four patients will be recruited for the study (67 for each arm) and with an anticipated attrition rate of 20-25%, one hundred patients will finally be studied.
Main Inclusion Criteria	
All adult lung cancer patients > 18 years diagnosed or suspected of non-small cell lung cancer (NSCLC) with surgically resectable disease, who are referred for pre-treatment optimization with Prehab from the lung cancer Multi-Disciplinary Teams (MDTs) across South West Wales (Swansea lung MDTs, the Hywel Dda lung MDTs and Princess of Wales lung MDT).
 
Lung cancer patient are referred for pre-treatment optimization with Prehab if they meet the following referral criteria: <math>\geq 1</math> Medical Research Council (MRC) dyspnoea score; or <math>\geq 1</math> World Health Organization (WHO)

	
performance status (PS); age <math>\geq 70</math> years or frailty index <math>>3</math>; borderline or poor pulmonary function (forced expiratory volume in one second (FEV1) or diffusion capacity for carbon monoxide (DLCO) <math><50\%</math>); sedentary patients despite having adequate FEV1 or DLCO. Patients will be included in the trial if they are capable of giving consent to participation and aged 18 and over.
 
Additionally, patients who have no contraindications to IMT use.

Statistical Methodology and Analysis	
Our aim is to evaluate the impact of thoracic Prehab with IMT compared to standard Prehab in reducing post operative pulmonary complications following surgical resection in lung cancer patients in a RCT.
 
Descriptive statistics will be used to summarise participants' characteristics and outcome measures.
 
Statistical analyses will be performed using SPSS statistical software, version 20.0 (IBM Corporation, Armonk, NY, USA). Two-sided significance tests will be used (<math>\alpha \leq 0.05</math>). Data will be presented as mean and standard deviation (SD), or median and interquartile range (IQR) for variables with a skewed distribution. Differences between groups in categorical variables will be tested with Chi square or Fisher's exact test. For continuous data the student's t test or the Mann-Whitney U test will be used. The Wilcoxon signed rank test will be used to compare MIP and QoL at T0 and T1 and T2. Relative risk will be calculated for post operative pulmonary complications (PPCs) graded 1-V using the Clavien Dindo classification and impact of IMT on the study group compared to the control group. Assuming a 36.7 incidence of PPC after surgery in the control arm and using a significance level of 0.05 and a power of 80%, 50 patients are required in each arm.

## Glossary of Terms and Abbreviations

AE	Adverse Event
AR	Adverse Reaction
ASR	Annual Safety Report
BACPR	British Association for Cardiovascular Prevention and Rehabilitation
CA	Competent Authority
CI	Chief Investigator
COPD	Chronic Obstructive Pulmonary Disease
CRF	Case Report Form
CRO	Contract Research Organisation
DLCO	Diffusion capacity for carbon monoxide
DMC	Data Monitoring Committee
EC	European Commission
EORTC	European Organization for Research and Treatment of Cancer
FEV1	Forced expiratory volume in one second
FITT	Frequency, Intensity, Type and Time principles of training
GAfREC	Governance Arrangements for NHS Research Ethics Committees
GCP	Good Clinical Research Practice
HLOS	Hospital length of stay
HRQol	Health related quality of life
IASLC	International Association for the Study of Lung Cancer
ICF	Informed Consent Form
IQR	Interquartile range
IMT	Inspiratory muscle trainer
IS	Incentive spirometry
IP	Intellectual Property
ISRCTN	International Standard Randomised Controlled Trial Number
LHC	Lung Health Check
LOA	Levels of activity
LOHS	Length of hospital stay
MDT	Multi-Disciplinary team
MIP	Maximal Inspiratory Pressure
MRC	Medical Research Council dyspnoea score
Main REC	Main Research Ethics Committee

NHS	National Health Service
NHS R&D	National Health Service Research & Development
NICE	National Institute for Health and Care Excellence
NSCLC	Non-small cell lung cancer
PI	Principle Investigator
PIS	Patient Information Sheet
PPI	Patient and public involvement representatives
PPC	Post-operative pulmonary complication
Prehab	Thoracic Prehab Programme
PREM	Patient reported experience measure
PROM	Patient reported outcome measure
PS	World Health Organization Performance Status
QA	Quality Assurance
QALY	Quality adjusted life years
QC	Quality Control
QOL	Quality of life
Participant	An individual who takes part in a clinical trial
RCT	Randomised Controlled Trial
REC	Research Ethics Committee
REDCap	Research Electronic Data Capture
SAE	Serious Adverse Event
SBUHB	Swansea Bay University Health Board
SCTC	Society of Cardiothoracic Surgery
SDV	Source Document Verification
SOP	Standard Operating Procedure
SSA	Site Specific Assessment
TMG	Trial Management Group
TSC	Trial Steering Committee
UK	United Kingdom
WHO	World Health Organization
6MWT	6 minute walk test

## 1. Introduction

### 1.1. Background

Lung cancer is the most common cause of cancer-related deaths in Wales (1). Although surgical resection for early-stage lung cancer with curative intent remains the primary treatment, patients with significant smoking related underlying cardiopulmonary disease and impaired pulmonary function, dyspnoea, frailty and decreased activity levels are unfit for surgery and referred for alternative treatment (2,3). Secondly, individuals who proceed to lung resection, thoracic surgery and general anaesthesia may have direct effects on their respiratory system potentially leading to postoperative pulmonary complications (PPCs), which increases hospital morbidity, prolongs hospital length of stay (HLOS) impacts on the quality of life (QOL) of patients and adds to health-care costs (4). Our aim is to evaluate whether incorporating a breathing training device, POWERBreathe into the existing standardised thoracic prehabilitation program (Prehab) will optimise unfit patients physically for surgery, and following surgery reduce their risk of developing PPC's, reduce HLOS and improve QOL of patients and improve service outcomes (5).

The PRIMROSE study aims to compare two groups of patients referred for Prehab who have lung cancer treatable with surgery: (A) standard Prehab and training with the inspiratory muscle training (IMT) device; and (B) standard Prehab alone, in non-small cell lung cancer patients (NSCLC) undergoing lung resection surgery, with clear primary and secondary outcome measures.

One hundred and thirty-four patients will be recruited for the study (67 for each arm) and with an anticipated attrition rate of 25%, one hundred patients will finally be studied (6,7). With 134 recruited and an attrition rate of 25%, only 100 will remain (50 in each arm). The primary outcome measure tested will be the proportion of patients in each group experiencing postoperative pulmonary complications (PPC), which will be graded I-V using the Clavien Dindo Classification (8). PPCs will be broadly classified as minor (grade 1) and major complications (grade 2-5 where 5 is death). What we want to learn from this RCT study is whether IMT helps reduce grade  $\geq 2$  PPCs to either grade 1 or no complications and thereby help shorten the length of stay in hospital for patients undergoing lung resection surgery.

Secondary outcome measures tested will be Medical Research Council (MRC) dyspnoea score, World Health Organization (WHO) performance status (PS), levels of activity (LOA),

thoracoscore, frailty index (FI), six-minute walk distance test distance (6MWD), maximum inspiratory pressure (MIP) and quality of life (QoL) data using the EORTC QLQ-30 questionnaire (9). In addition, researchers will collect safety data on, complication rates, mortality and HLOS. The quality of Prehab delivery and outcomes will be closely monitored in accordance with good clinical practice in research guidelines.

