## 2. Objectives and Design

### 2.1. Trial Objectives

**Primary Objective:** A randomised controlled trial to evaluate the impact of thoracic PRehabilitation with Inspiratory Muscle tRaining cOmpared to Standard prEhabilitation in surgical lung cancer patients [PRIMROSE Trial].

**Recruitment rate:** The study aims to recruit 134 patients for randomisation over twelve months, with 67 randomised to the intervention group and 67 to the control group (6).

**Retention rate:** These are high-risk patients and a high attrition rate in this population is considered normal. We anticipate the retention of 50 patients in each arm following 1:1 randomisation, and is based on our previous study (15), which showed that following assessment, 6.8% NSCLC patients fail to attend Prehab and 1.1% died prior to commencing Prehab. Likewise, following Prehab, 75.8% patients are ready to proceed with surgery. The attrition rate is an estimate and is anticipated attrition to be 20%-25%.

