## 2.2. Trial Design:

This is a randomised controlled PRIMROSE trial. This trial will be single centred, as there are very few centres in the United Kingdom (UK) that deliver this highly specialised service.

Study population: Lung cancer patients with surgically resectable disease referred for pre-treatment optimization with Prehab, from the lung cancer Multi-Disciplinary Teams (MDT's) across South West Wales. Eligible patients will be randomised to the trial on a 1:1 ratio to either the intervention arm or control arm [figure 4].

Participants in group A will receive standard Prehab and training with the IMT device (POWERBreathe); participants in group B will receive standard Prehab alone.

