**Post-discharge assessment:** Our primary objective is to determine whether IMT prior to surgery with Prehab helps reduce PPC following surgery, which is up to the point of discharge from hospital (alive or dead). This is one time point. Hence, it is anticipated that all patients will complete the discharge assessment for complications. Thus, the study is not underpowered for the primary end point.

Mortality rates will be collected at discharge, 1 month, 3 months, and 365 days post-surgery.

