## **7. Statistical Considerations**

### **7.1. Primary Endpoint Efficacy Analysis**

To test our primary hypothesis the chi-square test will be used to assess whether IMT in combination with Prehab is effective in reducing PPCs following lung resection surgery compared with its control i.e., standard Prehab using a significance level of 0.05. 4x4 matrix.

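### The primary outcome reads as a PPC of any grade, but the stated question concerns grade 2 or higher; and two arms cannot form the 4x4 table named for the primary test

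*Protocol*

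**What the plan says.** Section 1.1 makes three statements in sequence. It defines the outcome: "The primary outcome measure tested will be the proportion of patients in each group experiencing postoperative pulmonary complications (PPC), which will be graded I-V". The grading scale is Clavien-Dindo. It divides the grades in two, with grade 1 minor and grades 2 to 5 major. It then gives the question, which opens "What we want to learn from this RCT study is whether IMT helps reduce grade", names complications of grade 2 or higher, and speaks of bringing these "to either grade 1 or no complications and thereby help shorten the length of stay in hospital".

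No other section sets a threshold.

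- The Primary Objective in section 2.1 repeats the trial title and names no outcome: "A randomised controlled trial to evaluate the impact of thoracic PRehabilitation with Inspiratory Muscle tRaining cOmpared to Standard prEhabilitation in surgical lung cancer patients".
- The post-discharge paragraph of section 2.4.1 says only: "Our primary objective is to determine whether IMT prior to surgery with Prehab helps reduce PPC following surgery".
- The synopsis and sections 2.4.2 and 7.5 plan a relative risk for PPCs graded I to V.
- Section 2.4.1 assumes a 36.7% control incidence of PPC without saying which grades it covers.

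Section 7.1 specifies a chi-square test of whether IMT reduces PPCs, "using a significance level of 0.05. 4x4 matrix". Section 2.2 describes two arms: "Eligible patients will be randomised to the trial on a 1:1 ratio to either the intervention arm or control arm".

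**The concern.** The definition and the question treat a grade 1 complication differently. If any PPC graded I to V counts, a grade 1 patient is an event. In the question, grade 1 is one of the two results the intervention is meant to achieve. Whether grade 1 counts decides what the primary test measures.

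The operative text favours the any-grade reading. If it is followed, any benefit that takes the form of milder complications, rather than fewer patients with complications, drops out of the primary comparison. If the threshold stays open until the data are seen, two defensible analyses of the same data could reach different conclusions.

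The 4x4 table is a smaller matter. Section 7.1 is where the primary test is specified and could have shown whether grades are to be dichotomised. As written, the table cannot be built.

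**Working it through.** **1. Which event each section implies**

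| Section | Wording in substance | Threshold |
|---|---|---|
| 1.1, outcome | proportion with a PPC, graded I to V | none |
| 1.1, question | grade 2 or higher brought to grade 1 or none | grade 2 |
| 2.1 | trial title | no outcome named |
| 2.4.1, post-discharge paragraph | reduce PPC | none |
| 2.4.1, sample size | 36.7% incidence of PPC | none |
| Synopsis, 2.4.2, 7.5 | relative risk, PPCs graded I to V | none |
| 7.1 | chi-square, reducing PPCs | none |

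Grade 2 or higher appears only in section 1.1, and never as the event to be tested.

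**2. What an any-grade count can register**

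In one arm let *b* patients have grade 1 and *c* have grade 2 or higher. The any-grade count is *b* + *c*. If *m* patients move from grade 2 or higher to grade 1, it becomes (*b* + *m*) + (*c* − *m*) = *b* + *c*, unchanged for every *m*. Only moves to no complication lower it. The grade 2 or higher count falls by *m*.

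**3. Size in an example (hypothetical counts, 50 per arm)**

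Control: 18 PPCs, all grade 2 or higher. IMT: 18 PPCs, 6 of grade 2 or higher and 12 of grade 1.

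- Any grade: 18 v 18, relative risk 1.00, chi-square 0, p = 1.00.
- Grade 2 or higher: 18 v 6. The pooled rate is 24/100 = 0.24. Pearson chi-square without correction = (0.36 − 0.12)² / [0.24 × 0.76 × (2/50)] = 0.0576 / 0.007296 = 7.89 on 1 df, p = 0.005 (Fisher 0.009).
- Relative risk = 0.12/0.36 = 0.333. The standard error of its log is √(1/6 − 1/50 + 1/18 − 1/50) = 0.427, so the 95% CI is exp(−1.099 ± 1.96 × 0.427) = 0.14 to 0.77.

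The reverse is also possible. With control at 6 of grade 2 or higher plus 12 of grade 1, and IMT at 6 of grade 2 or higher and no grade 1, any grade is 18 v 6 (p = 0.005) while grade 2 or higher is 6 v 6 (relative risk 1.00).

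**4. The table**

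Degrees of freedom are (rows − 1) × (columns − 1). Arm by event is 2x2, 1 df. Arm by none, minor or major is 2x3, 2 df. Arm by none and grades I to V is 2x6, 5 df. A 4x4 table has 9 df and needs four rows, but there are two arms.

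**5. The sample size**

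The text gives no IMT-arm rate and Figure 5 is not shown, so 50 per arm cannot be reproduced directly; it can be solved backwards. With two-sided 0.05 and pooled variance under the null,

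power = Φ{ [(p₁ − p₂) − 1.96 √(2p̄(1 − p̄)/n)] / √([p₁(1 − p₁) + p₂(1 − p₂)]/n) }.

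With p₁ = 0.367, p₂ = 0.128 and n = 50, this is Φ[(0.239 − 1.96 × 0.0863)/0.0829] = Φ(0.84) = 0.80. So 50 per arm corresponds to 36.7% v about 12.8%, a relative risk of 0.349. Other two-sided forms give 11.1% (continuity-corrected) or 13.3% (unpooled).

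If 36.7% is an any-grade rate and any grade is kept, nothing changes. If it is an any-grade rate and grade 2 or higher is chosen, the control rate becomes 0.367 × (1 − g), where g is the share of control PPCs that are grade 1. The documents do not give g, so a range is assumed:

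| Assumed g | Control rate, grade 2+ | Power at relative risk 0.349 | IMT rate detectable with 80% power |
|---|---|---|---|
| 10% | 33.0% | 74% | 10.2% |
| 25% | 27.5% | 64% | 6.7% |
| 50% | 18.4% | 44% | 1.7% |

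**The case against.** The strongest reply is that section 1.1 can be read as one definition: PPCs are graded, split into minor and major, and the split identifies the event of interest. The protocol never says any grade, and on this reading only a threshold clause is missing. That is possible, but nothing else in the protocol supports it. The sections that set the test and the effect measure carry no cut-off, and the relative risk explicitly spans grades I to V.

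A second reply is that the primary test need not be binary. A 2x3 table of the first example (none/minor/major, 32/0/18 v 32/12/6) gives expected counts of 32, 6 and 12 per arm and chi-square = 2 × 36/6 + 2 × 36/12 = 18.0 on 2 df, p = 0.0001, so the shift would show. The arithmetic is right, but the protocol does not specify that table, and its outcome is a proportion.

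Three points stand. The example counts are extreme, and they set a null result against a benefit rather than effects in opposite directions. The power figures rest on an assumed share and an assumed equal relative risk. The 4x4 wording is probably a slip and would not by itself alter a result. None of these removes the conflict over grade 1. Nor is it a detail to leave to an analysis plan: the primary event is a protocol matter, and here the protocol states it inconsistently.

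**Conclusion.** The concern holds. The outcome as labelled and the question as stated disagree on whether grade 1 is an event, and no section settles it. That an any-grade count misses a move to grade 1 follows by arithmetic and needs no assumption. How much this would matter in the trial depends on the mix of grades, which the documents do not give; the example shows that the gap can run from no difference to a relative risk of 0.33 in the same patients. The 4x4 table is wrong as written but minor.

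The documents do not show that 36.7% or 50 per arm is wrong. The power range of 74% to 44% applies only if 36.7% is an any-grade rate, grade 2 or higher is chosen, and the assumed shares and relative risk hold. It does not measure an actual loss. The point should be fixed; it does not threaten the trial if fixed in time.

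**What to change.** Name one binary primary event with its Clavien-Dindo threshold, in a dated amendment made before outcomes are examined by arm. Two choices are open to the sponsor: grade 2 or higher, which matches the question in section 1.1; or any grade, with that question reworded. Use the chosen event in the synopsis and in sections 1.1, 2.4.1, 2.4.2, 7.1 and 7.5, and report the other as secondary. In section 7.1 replace the 4x4 table with a 2x2 table of arm by event, with the relative risk and its 95% CI. State which grades the 36.7% covers; if they differ from the chosen event, restate the power or the detectable difference at 50 per arm.

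The cost is small. Keeping any grade needs one reworded sentence in 1.1, a threshold clause and the corrected table. Choosing grade 2 or higher changes wording in six places and may mean accepting lower stated power or a larger detectable difference. Timing matters: section 3.1 planned recruitment from January 2025, and section 8.4 has the chief and principal investigators reviewing data monthly.

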## 1.2. Preclinical Data

[figure not shown]
Lung cancer treatment has complex and critical challenges as highlighted by The Welsh NHS Confederation (2015), the Welsh Government Parliamentary Review of Health and Social Care in Wales (2018) and A Healthier Wales (2018) (10,12). These include shifting demographics, an ever-ageing population and increased prevalence of complex and chronic conditions alongside fiscal constraints. For example, 63% of patients with lung cancer have chronic obstructive pulmonary disease (COPD), resulting in breathlessness and poor exercise tolerance and predispose surgical patients to post-operative pulmonary complications (PPC's) increased morbidity, longer hospital length of stays (HLOS) and mortality (4,13)

Smoking accounts for about 90% of all lung cancer cases (13). Patients with resectable NSCLC may have smoking related underlying cardiopulmonary disease causing significant dyspnoea (due to impaired or poor pulmonary function), impaired performance status (PS) and impaired levels of activity (LOA) (14,15). Loss of lung tissue in deconditioned NSCLC patients may grossly impair their postoperative ventilatory function, predisposing them to significant dyspnoea and cardiopulmonary complications. These patients are considered high-risk for surgery or inoperable and referred for radiotherapy, systemic anticancer treatment, or palliative care instead (2-4, 13-15). In Wales, an average of only 17% of patients undergo lung resection annually (16).

Of those individuals who proceed to lung resection, thoracic surgery and general anaesthesia may have direct effects on their respiratory system predisposing patients to PPCs, which increases hospital morbidity, prolongs HLOS and adds to health-care costs (4). PPCs in patients for thoracotomy and lung resection with chronic lung disease have been reported to be as high as 30% (4). Decreased lung expansion due to poor inspiratory muscle strength (respiratory muscle weakness) causes atelectasis and PPCs (4). Reduced respiratory muscle function along with reduced mucociliary function and bacterial proliferation promote colonisation of the respiratory tract by bacteria leading to pneumonia and acute respiratory distress syndrome with patients requiring intensive care treatment and longer HLOS, which

increase National Health Service (NHS) costs, places pressures on critical care beds and increases mortality (4).

Annually published lung cancer audit data for Wales consistently demonstrates a wide variation in the number of NSCLC patients receiving surgery with curative intent across the eight lung cancer Multi-Disciplinary Teams (MDT's) across South Wales (16). Fitness for surgery and area of deprivation of patients play a major role in this variation. The Equality Act (2010) advocates equality of opportunity. The SBUHB Prehab service, ensures that male and female patients, elderly patients and patients with diverse backgrounds are given the same opportunities to access high quality of surgical care and support. Hence, our proposed research project aims to ensure that vulnerable, high-risk, unfit NSCLC patients with surgically resectable disease are not denied curative surgery and instead will benefit by receiving surgery. Furthermore, to ensure equity in provision of surgical care to patients requiring thoracic surgery, the Welsh Government aims to establish a South Wales Adult Thoracic Surgical Service based at Morriston Hospital, Swansea by 2027. The aim of our SBUHB Prehab service is to ensure that there is equity in the provision of a standardised, evidence based Prehab service to all patients across South Wales especially when referrals from all South Wales Health Board lung MDTs commence to the thoracic SBUHB Prehab service by 2027 (Figure 1).

